9. SAFETY EVALUATION

9.1. Adverse Events

Verbatim AE terms will be coded to a SOC and PT using MedDRA Version 21.0 or later.

All analyses of AEs will be based on the principle of treatment emergence. An AE is considered to be treatment-emergent if it has a start date on or after the date of the first dose of study treatment. In general, if the treatment emergence of an AE is not clear due to a missing or incomplete AE start date, the AE will be considered to be treatment-emergent unless the non-missing portions of the start date and the end date indicate otherwise.

In general, whenever a tabular summary of AEs is mentioned in this document, it is intended that the tabular summary is in reference to TEAEs, even though “treatment-emergent” may not be explicitly mentioned. By-subject data listings of AEs will include all events regardless of treatment emergence and TEAEs will be identified.

Counting will be at the subject level for each level of summarization (e.g., any AE, SOC, and PT), with subjects experiencing more than one AE counted only once. In the summary of AEs by severity (mild, moderate, severe), subjects will be counted once at the highest severity reported at each level of summarization. AEs that are missing severity will be presented in summary tables as “Missing”. AEs that are missing relationship to study treatment will be presented in summary tables as “Related”.

The following summaries will be presented for the safety population:

- Overall Summary of AEs - showing the number and percent of subjects with an AE; a moderate or severe AE; a severe AE; a SAE; a treatment-related AE; a treatment-related SAE; an AE leading to discontinuation of study treatment; an AE leading to withdrawal from study; an AE resulting in death; and an AE of interest (as defined in [Protocol Section 10.3.3](#)).
- Incidence of AEs by SOC and PT
- Incidence of AEs by PT
- AEs with Incidence $\geq 5\%$ in Either Treatment Group by PT
- AEs with Incidence at Least $\geq 3\%$ Higher in the GB001 40 mg Group Relative to the Placebo Group by Preferred Term
- Incidence of SAEs by SOC and PT
- Incidence of AEs by SOC, PT, and Maximum Severity
- Incidence of Treatment-Related AEs by SOC and PT
- Incidence of AEs Leading to Discontinuation of Study Treatment by SOC and PT
- Incidence of AEs Leading to Withdrawal from Study by SOC and PT
- Summary of Pruritus AEs

- Incidence of Liver Chemistry AEs by PT
- Incidence of Liver Chemistry AEs Leading to Discontinuation of Study Treatment by PT
- Incidence of AEs of Interest by SOC and PT

All AEs, AEs leading to discontinuation of study treatment and/or withdrawal from study, AEs of interest, SAEs, and AEs resulting in death will be presented in by-subject data listings.

9.2. Clinical Laboratory Evaluation

Actual values and change from baseline values for quantitative laboratory parameters (clinical and liver chemistry, hematology, and urinalysis) will be summarized by visit for the safety population.

Shift tables will be presented for clinical and liver chemistry, hematology, and qualitative urinalysis parameters summarizing shifts from baseline to high and low (or to abnormal for urinalysis) at any time post-baseline based on laboratory normal ranges.

A summary of maximum post-baseline values > 1.0 , > 1.5 , and $> 3.0 \text{ } 10^9/\text{L}$ for blood eosinophils will be presented.

Summaries of maximum post-baseline values for liver chemistry parameters (alanine aminotransferase [ALT], aspartate aminotransferase [AST], ALT or AST, concurrent ALT or AST and total bilirubin, total bilirubin, direct bilirubin, indirect bilirubin, alkaline phosphatase, gamma-glutamyl transferase [GGT]), and bile acid according to categories based on multiples of upper limit of normal (ULN) will be presented. Liver chemistry parameters according to categories based on multiples of ULN will also be presented by visit.

For laboratory shift tables and summaries of maximum post-baseline values, only subjects with at least one post-baseline value will be included.

The time to first elevation for ALT will be presented for subjects with an elevation in ALT. An elevation for ALT will be defined as the first post-baseline value $\geq 1.5 \times \text{ULN}$ for subjects with a baseline value $\leq \text{ULN}$, and the first post-baseline value with a $> 50\%$ increase from baseline for subjects with a baseline value $> \text{ULN}$. This analysis will also be repeated using a threshold of $> 1.0 \times \text{ULN}$. In addition, the time to first elevation of AST will be summarized in the same manner as described above for time to first elevation of ALT.

In addition, the following figures/plots will be provided:

- Mean change from baseline values, including SE bars, by visit figures for liver chemistry parameters
- Mean ratio of actual values to ULN, including SE bars, by visit figures for liver chemistry parameters
- Evaluation of Drug-Induced Serious Hepatotoxicity (eDISH) ([Merz, 2014](#)) plots

- Mean actual values and mean change from baseline values, including SE bars, by visit figures for blood eosinophils
- Maximum post-baseline values versus baseline values plot for blood eosinophils

Laboratory parameters will also be presented in by-subject data listings. In addition, liver event information including liver biopsy and liver imaging results will be presented in a by-subject data listing.

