2.3. Benefit/Risk Assessment

2.3.1. GB001 Benefit/Risk Assessment

GB001, an oral DP2 antagonist, is being developed as a controller therapy in asthma. The clinical development of GB001 includes 9 completed clinical studies and 2 ongoing clinical studies.

As of 29 August 2019, a total of 459 subjects have received at least 1 dose of GB001 at any dose level. Of these, 98 subjects received a single dose of GB001 ranging from 1 mg to 200 mg, and 361 subjects received multiple doses from 5 mg to 160 mg. Of the 361 subjects who received multiple doses, about half (n = 159) were subjects with asthma in the completed Phase 2 studies who received either GB001 20 mg for up to 12 weeks, including 2 weeks with concurrent dosing of montelukast 10 mg daily (Study ADC3680-07), or GB001 22.73 mg daily for up to 4 weeks (Study ADC3680-04) or up to 16 weeks concurrent with ICS withdrawal and discontinuation (Study PTR-36-201).

Based on evaluation of asthma worsening (Study PTR-36-201), GB001 at a 20 mg dose showed efficacy in the overall population and the greatest efficacy in the subgroup of patients with eosinophil counts \geq 300 cells/ μ L. This is consistent with the current understanding of the biology regarding this pathway.

As of 29 August 2019, a total of 459 subjects have received at least 1 dose of GB001 at any dose level. Drug induced liver injury is considered a potential risk of GB001 due to the occurrence of two Hy's Law cases, one was a liver disorder (preferred term) in a healthy subject at 160 mg in Study PTR-36-101 and one was hepatic enzyme increased (preferred term) in Study GB001-2001 which remains blinded. Details are provided in the IB. Liver monitoring is critical for the safe management of subjects. Investigators should have a low threshold for discontinuing study drug with any suspicion of drug-induced liver injury. Safety will be closely monitored by the Sponsor.

In a study with another DP₂ antagonist (OC000459) which evaluated 35 subjects allergic to grass pollen, subjects were exposed to grass pollen for 6 hours on the 2nd and 8th days of treatment. During the first treatment period, there was a significant reduction in the total nasal symptom score compared with placebo ([Horak, 2012](#)). These data support the role of DP₂ in upper airway disease and provide a foundation for potential therapeutic benefits by blocking this pathway in patients with upper airway inflammatory disease.

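### Time to first ALT or AST elevation is summarised only among subjects who had one, so it describes latency in cases and does not estimate the hazard or cumulative onset by treatment

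*SAP*

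**What the plan says.** SAP 9.2 (Clinical Laboratory Evaluation) says: "The time to first elevation for ALT will be presented for subjects with an elevation in ALT".

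- **Event.** "An elevation for ALT will be defined as the first post-baseline value" at or above 1.5 x ULN when baseline is no higher than ULN. When baseline is above ULN, the event is a rise of more than 50%.
- **Second threshold.** "This analysis will also be repeated using a threshold of" more than 1.0 x ULN.
- **AST.** "the time to first elevation of AST will be summarized in the same manner as described above" for ALT.

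For these displays the section states no at-risk denominator, censoring rule, Kaplan-Meier curve or between-group estimate.

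The same section plans other liver displays that are not restricted to cases. They are maximum post-baseline values by multiples of ULN, shift tables, mean plots by visit and eDISH plots. For the shift tables and maximum-value summaries, "only subjects with at least one post-baseline value will be included". In addition, "Liver chemistry parameters according to categories based on multiples of ULN will also be presented by visit". SAP 9.1 adds the incidence of liver chemistry AEs and of AEs of interest.

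**The concern.** Selecting subjects on a post-randomization outcome and then describing their event times removes the information that distinguishes one hazard from another, namely how many subjects at risk had the event and how many did not. A drug that raises the hazard by a constant factor produces more cases but hardly changes when they occur.

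Onset timing matters here. Protocol 2.3.1 says: "Drug induced liver injury is considered a potential risk of GB001 due to the occurrence of two Hy's Law cases". The schedule of activities collects chemistry weekly through Week 6, and the amendment history gives closer laboratory monitoring in the first month after starting treatment as the reason for adding the Week 1 and Week 3 visits. The data for an onset curve are therefore collected, but the only planned time-to-onset analysis of liver enzymes does not use them that way.

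**Working it through.** The documents give no figure for this display, so there is nothing to reproduce. The check has an arithmetic part and a comparison with the SAP's own practice. All incidences and hazard ratios below are assumptions. The documents supply about 50 subjects per group (SAP 2.5), 16 weeks of treatment, and post-baseline chemistry at Weeks 1, 2, 3, 4, 5, 6, 8, 12 and 16 (Protocol 1.3).

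**1. Mean time among cases under a constant hazard.** With 16-week incidence p:

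- λ = −ln(1 − p)/16
- mean among cases = 1/λ − 16(1 − p)/p
- hazard ratio = ln(1 − p₁)/ln(1 − p₀)

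| p | λ per week | 1/λ | 16(1 − p)/p | Mean, weeks | HR vs 5% | Expected cases per 50 |
|---|---|---|---|---|---|---|
| 5% | 0.05129/16 = 0.003206 | 311.93 | 304.00 | 7.93 | 1 | 2.5 |
| 15% | 0.16252/16 = 0.010157 | 98.45 | 90.67 | 7.78 | 0.16252/0.05129 = 3.17 | 7.5 |
| 25% | 0.28768/16 = 0.017980 | 55.62 | 48.00 | 7.62 | 0.28768/0.05129 = 5.61 | 12.5 |

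The hazard changes more than fivefold and the mean moves by about 0.3 weeks.

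**2. A different hazard shape.** Keep 5% against 15%, but let the extra 10% on GB001 arise evenly over Weeks 0 to 6 (mean 3 weeks). The GB001 mean among cases is (5 × 7.93 + 10 × 3)/15 = 4.64 weeks, against 7.93 on placebo. The display would then show a difference.

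**3. Detection at the scheduled visits.** This uses constant hazards, 50 per arm, no dropout and 4,000 simulated trials per row. The SAP states no test for this display; the rejection rates (two-sided 0.05) only gauge how much information each approach carries.

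| Placebo risk | HR | Expected cases, placebo / GB001 | Mean detection day among cases | Rank test, cases only | Log-rank, all subjects | Fisher test of incidence |
|---|---|---|---|---|---|---|
| 10% | 1 | 5.0 / 5.0 | 64.6 / 64.6 | 3% | 5% | 2% |
| 10% | 3 | 5.0 / 13.5 | 64.6 / 62.4 | 3% | 62% | 52% |
| 10% | 5 | 5.0 / 20.5 | 64.6 / 60.2 | 4% | 96% | 93% |
| 4% | 5 | 2.0 / 9.2 | 65.2 / 63.6 | 2% | 66% | 50% |

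The median detection day among cases is Day 57 in both arms in every row. Under constant hazards, times among cases carry almost no information about the treatment difference. The analysis of all subjects does, and so does plain incidence.

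**4. The SAP's own practice.** For time to first NPS response and first CRS exacerbation, SAP 8.3.2.2 keeps subjects without the event, censors them at their last assessment, and uses Cox models and Kaplan-Meier summaries. SAP 9.2 gives no reason for handling liver onset differently.

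**The case against.** A reader might infer that the SAP could miss a liver excess, or that the two arms would look alike in this display. The documents do not support either.

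- **Counts remain visible.** SAP 3 reports n with every continuous summary and presents safety tables by actual treatment group, and SAP 5.1 gives population sizes by group. At 5% against 15%, about 2.5 against 7.5 cases would be expected. Only the mean times would look alike.
- **Excess risk is covered elsewhere.** The displays in SAP 9.1 and 9.2 listed above are not case-restricted. For a subject normal at baseline, a shift to high at any time is essentially the more-than-1.0 x ULN event, so its incidence is already tabulated.
- **Some timing is covered.** ULN categories by visit show when elevations are present, although that is prevalence among those measured and not first onset.
- **The near-equal means depend on constant hazards.** Step 2 shows an early excess shifting them.
- **Early stopping is a limited worry.** Protocol 4.1.1 and 7.1 ask subjects who stop study treatment to stay for the remaining visits, so stopping treatment does not by itself end ALT follow-up.
- **The display is descriptive.** The SAP attaches no test or estimate to it, and a summary of latency among cases is legitimate as such.

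All of this stands and narrows the point. None of it supplies time to first onset over all subjects at risk. Maximum-value tables are crude proportions that ignore unequal follow-up (SAP 2.5 assumes 15% dropout), and no planned table states n/N for the baseline-dependent definition of elevation.

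**Conclusion.** The point holds in a limited form. The ALT and AST time-to-elevation displays, at both thresholds, condition on the event and estimate neither hazard nor cumulative onset by treatment. Under constant hazards and assumed incidences of 5% and 15%, a hazard ratio of about 3.2 leaves the means at 7.9 and 7.8 weeks; an early-onset excess would separate them.

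It would be wrong to conclude that the plan cannot reveal a liver signal. The displays that are not limited to cases can reveal one, and in the simulations an incidence comparison recovered much of what the log-rank test did (50 to 93% against 62 to 96%). The gap is confined to time to first onset over subjects at risk. The primary efficacy conclusion is not affected. This is a cheap improvement to one display, worth making because it concerns the drug's stated liver risk.

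**What to change.** In SAP 9.2, for ALT and AST and for both thresholds, add Kaplan-Meier (cumulative incidence) curves by actual treatment group. Include every safety-population subject with a post-baseline value of that enzyme, and censor those without an elevation at their last liver chemistry. Print n/N and numbers at risk. Keep the present case-only summary as a supplement, labelled as latency among cases. Any hazard ratio should be optional and descriptive.

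The randomization criteria require ALT and AST no higher than ULN at screening, so most subjects should fall under the first branch of the elevation definition and the at-risk set is simple to form.

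The cost is a few lines of SAP text and one or two extra figures from data already collected. The downside is imprecision: with about 50 subjects per group and few events expected, the curves will have wide intervals and should be read as description.

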9.3. Vital Signs and Other Observations Related to Safety

9.3.1. Vital Signs

Actual values and change from baseline values for vital sign parameters (systolic and diastolic blood pressure, pulse rate, respiratory rate, temperature, and weight) will be summarized by visit for the safety population.

A summary table of the incidence of abnormalities in vital sign parameters will be presented according to the following abnormality criteria.

Table 2: Vital Sign Parameter Abnormality Criteria

Vital Sign Parameter	Abnormality Criteria
Systolic Blood Pressure	High or Increased: > 180 mmHg post-baseline if ≤ 180 mmHg at baseline, or an increase from baseline of > 40 mmHg. Low or Decreased: < 90 mmHg post-baseline if ≥ 90 mmHg at baseline, or a decrease from baseline of > 30 mmHg.
Diastolic Blood Pressure	High or Increased: > 105 mmHg post-baseline if ≤ 105 mmHg at baseline, or an increase from baseline of > 30 mmHg. Low or Decreased: < 50 mmHg post-baseline if ≥ 50 mmHg at baseline, or a decrease from baseline of > 20 mmHg.
Pulse Rate	High or Increased: > 120 bpm post-baseline if ≤ 120 bpm at baseline, or an increase from baseline of > 20 bpm. Low or Decreased: < 50 bpm post-baseline if ≥ 50 bpm at baseline, or a decrease from baseline of > 20 bpm.
Temperature	> 38 degrees C and an increase from baseline of at least 1 degree C.

bpm = beats per minute

Vital sign parameters will also be presented in a by-subject data listing and abnormalities will be flagged.

9.3.2. Other Safety Measures

9.3.2.1. Electrocardiograms

Actual values and change from baseline values will be summarized by visit for the safety population for the following quantitative ECG parameters: heart rate, PR interval, QRS duration,

QT interval (uncorrected), Fridericia's correction formula for QT interval (QTcF), and RR interval.

Outlier analyses for QTcF intervals will be performed. This will consist of a summary of the number and percent of subjects with a post-baseline QTcF interval greater than 450 msec, 480 msec, and 500 msec and the number and percent of subjects with an increase from baseline in QTcF interval of greater than 30 msec and 60 msec.

Each ECG will be assessed with an overall interpretation of normal, abnormal, or unable to evaluate. Shift tables for overall interpretation will be presented, summarizing shifts from baseline to abnormal at any time post-baseline.

ECG parameters will also be presented in a by-subject data listing and outliers will be flagged.

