10. **ECG Assessment:** Subjects with QTcF \geq 450 msec for males or QTcF \geq 470 msec for females on the Screening visit ECG. However, if QTcF is above this prespecified limit and there are no other clinically significant ECG abnormalities in the opinion of the Investigator, the assessment can be repeated in triplicate. The triplicate QTcF values should be averaged by the Investigator to determine eligibility of the subject to enter the Run-in period. However, if any of the triplicate ECGs show a clinically significant abnormality in the opinion of the Investigator, the subject should be excluded, regardless of the average QTcF of the triplicates.
11. **Alcohol/Marijuana/Illlicit Drugs/Substance Abuse:** A known or suspected history of alcohol misuse, marijuana, illicit drugs, or substance abuse within 12 months prior to Screening visit.
12. **Smoking history:** Asthma or COPD patients that are current smokers (any substance), or former smokers with a smoking history of \geq 10 pack-years [(number of cigarettes per day/20) \times number of years smoked]. A former smoker is defined as a subject who quit smoking at least 6 months prior to Screening visit. This includes electronic cigarettes and vaping.
13. **Immunodeficiency:** A known immunodeficiency, including that due to human immunodeficiency virus (HIV), other than that explained by systemic corticosteroid use.
14. **Investigational medications:** Subjects who have received treatment with an investigational medication within the past 30 days or within 5 half-lives of the

medication, whichever is longer, prior to Screening visit (this also includes investigational formulations of marketed products).

- 15. Receiving prohibited medications:** Refer to Appendix 10 ([Section 10.10](#)) for more details.
 - a. Regular use of systemic corticosteroids or immunosuppressive therapies including methotrexate or azathioprine
 - b. Monoclonal antibodies used in the treatment of asthma
 - c. Medications, food or drink that are moderate or strong CYP3A4 inhibitors or inducers
 - d. Other medications that have the potential for interaction with GB001
 - e. Medications that have a black-box warning for hepatic toxicity.
- 16. Prior participation in a study with GB001:** Subjects who previously participated in a study with GB001 (also named PTR-36 or ADC3680).

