5.3. Randomization Criteria

Subjects must fulfill the following criteria to be randomized to study treatment:

1. **Diary compliance:** Compliance with completion of the Diary as defined as:
 - a. Completion of questions on 4 or more of the last 7 days immediately prior to Visit 2 (includes the morning of Visit 2).
 - b. **Note:** If the Diary was completed on < 4 days due to technical challenges, the Visit 2 may be delayed up to an additional 3 days to allow for completion of the Diary parameters above.
2. **Eosinophilic Phenotype:** Subjects must meet at least one of the criteria below.
 - Blood eosinophil count ≥ 250 cells/ μ L obtained at Visit 1.
OR
 - Minimum NPS of 4 out of a maximum score of 8 with a score of at least 2 for each nostril as assessed by a blinded central reader. Subjects with an NPS of 1-3 are not eligible for randomization.
3. **CRS exacerbation:** Subjects who experience a CRS exacerbation during the Run-in period should have their Randomization Visit (Visit 2) delayed until the investigator considers the subject has returned to their baseline status. If a 4-week Run-in period has elapsed before the subject is back to baseline status, then the subject will be considered a Run-in failure. CRS exacerbation is defined in [Section 8.1.6](#).
4. **Laboratory abnormality:** No evidence of clinically significant abnormality in the hematological, biochemical, or urinalysis at Screening visit, as judged by the investigator.
5. **Hepatitis status:** No diagnosis of chronic hepatitis B or C, as evidenced by a negative hepatitis B surface antigen (HBsAg) or hepatitis C antibody screen at Screening visit.
6. **Chemistry and hematology obtained at Screening visit:**
 - ALT $\leq 1 \times$ the upper limit of normal (ULN)
 - AST $\leq 1 \times$ ULN
 - Alkaline phosphatase $< 2 \times$ ULN
 - Bilirubin $< 1 \times$ ULN
 - Absolute eosinophil count $< 1,500$ cells/ μ L
 - White blood cell count $< 15,000$ cells/ μ L
7. **Pregnancy test:** For WOCBP, both the serum pregnancy test at the Screening visit and the urine pregnancy test at Visit 2 must be negative.
8. **Use of MFNS:** Subject newly switched onto MFNS during screening should tolerate MFNS during Run-in.
9. **Nasal symptoms:** SNOT-22 score ≥ 17 as assessed at randomization.
10. **ECG overread:** ECG overread by the central ECG reader confirms the QTcF interval is < 450 msec for males or QTcF < 470 msec for females.

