In general, all analyses will be performed for the overall population, with the exception of efficacy endpoints based on NPS, which will be performed only for the randomized CRSwNP subgroup.

Disposition, demographic and baseline characteristics, significant protocol deviations, and medical history tables will be presented by randomized treatment group and will include an overall column combining both treatment groups. Prior and concomitant medication tables will be presented by either randomized treatment group or actual treatment group, depending on the analysis, and will include an overall column combining both treatment groups. Select analyses among these will be performed for the randomized CRSwNP and CRSsNP subgroups.

Efficacy tables will be presented by randomized treatment group only and select efficacy analyses will be performed for the randomized CRSwNP and CRSsNP subgroups. Safety tables will be presented by actual treatment group and select safety analyses will be performed for the actual CRSwNP and CRSsNP subgroups.

When appropriate, sorting in disposition, demographic, and baseline characteristics tables will be based on decreasing incidence within the overall column. In general, AE tables that are displayed by system organ class (SOC) and preferred term (PT) will be sorted by the internationally agreed order for SOC, and by decreasing incidence and then alphabetically for PT within the GB001 40 mg column. Otherwise, safety tables, when applicable, will be sorted by decreasing incidence within the GB001 40 mg column.

Assessments at the Randomization Visit are to be performed prior to the first dose of study treatment. Therefore, for all measures, the baseline value is defined as either the last non-missing value before the first dose of study treatment, the mean over the last 7 days of the Run-in period including the value on Day 1 (AM endpoints collected in the daily Diary), or the mean over the last 7 days of the Run-in period excluding the value on Day 1 (PM endpoints collected in the Diary).

If multiple evaluations occur on the same day, the average of these evaluations will be used for analysis excluding maximum post-baseline, abnormality, and outlier analyses.

For all shift from baseline analyses, percentages will be based on the number of subjects in each baseline category and also having at least one post-baseline measurement.

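### The QTcF > 450 msec count has no baseline condition, so a woman who enters at 451-469 msec and does not change is reported as a post-baseline outlier (minor)

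*SAP*

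**What the plan says.** SAP 9.3.2.1 (Electrocardiograms) defines two sets of QTcF outliers. The first is absolute: "subjects with a post-baseline QTcF interval greater than 450 msec, 480 msec, and 500 msec". It carries no condition on baseline and no sex-specific limit. The second is relative: "subjects with an increase from baseline in QTcF interval of greater than 30 msec and 60 msec". The section also summarizes QTcF values and change from baseline by visit, gives a shift table for the overall ECG interpretation (not for QTcF category), and lists ECG data by subject with outliers flagged.

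The entry limits differ by sex. Protocol 5.2 (exclusion 10) excludes men from 450 msec and women from 470 msec at Screening. Protocol 5.3 (criterion 10) requires that the central overread "confirms the QTcF interval is < 450 msec for males or QTcF < 470 msec for females".

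SAP section 3 defines baseline, for measures not taken from the diary, as "the last non-missing value before the first dose of study treatment".

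For vital signs, SAP Table 2 ties each blood pressure and pulse limit to baseline. The systolic limit, for example, is "> 180 mmHg post-baseline if ≤ 180 mmHg at baseline", with a large change from baseline as the alternative route into the same row.

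**The concern.** A count of post-baseline values above a limit is normally read as a count of abnormalities that arose on treatment. Here the lowest analysis limit, 450 msec, lies below the highest value at which women may enter. Part of the > 450 msec row can therefore describe who was enrolled, not what happened afterwards, and the table does not show which part.

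Protocol 9.4.2 promises counts of predefined abnormalities considered clinically significant. With about 50 subjects per arm the row will hold very few subjects, and sex is not a stratification factor. One or two women with long-standing values could form a visible share of it or create a chance difference between arms. What is at stake is how one descriptive safety row reads. No test or efficacy conclusion depends on it.

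**Working it through.** **1. Figure to reproduce.** There is none. The documents give no expected count, power or distribution for QTcF.

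**2. Overlap of entry limits and analysis limits.** For each sex, list whole-millisecond values v that are eligible (v < entry limit) and also exceed the analysis limit t (v > t).

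| Sex | Entry limit | t = 450 | t = 480 | t = 500 |
|---|---|---|---|---|
| Men | < 450 | none | none | none |
| Women | < 470 | 451-469 | none | none |

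The analysis limit is strict, so 450 itself is outside the overlap. Only one row is affected, and only through women.

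**3. Which ECG is the baseline.** The protocol's Schedule of Activities marks the 12-lead ECG at Screening and then late in treatment or at exit. As far as the extracted table can be read, none is marked at Randomization. The last value before first dose is then normally the Screening ECG, which is the reading to which the entry limits applied.

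**4. One subject followed through.** Take a woman with 460 msec at baseline and 460 msec at Week 16.
- Planned > 450 row: 460 > 450, so she is counted and flagged.
- Increase rows: 460 - 460 = 0, so she is not in the > 30 or > 60 msec counts.
- A rule of the Table 2 type (> 450 only if at or below 450 at baseline): not counted.

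**5. Rest of the SAP.** No other passage adds a baseline condition for QTcF. Elsewhere the SAP does allow for baseline: Table 2 for blood pressure and pulse, and section 9.2 for first ALT or AST elevation, where the definition depends on whether baseline exceeds the upper limit of normal.

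**6. Size, on assumed inputs.** None of these inputs is in the documents.
- Model: a subject's true level is T ~ N(mean, between-subject SD). Baseline is B = T + e1 and the single post-baseline value is P = T + e2, where e1 and e2 have the visit-to-visit SD.
- Keep B < 470 for women and B < 450 for men.
- Carry-over share = Pr(P > 450 and B > 450) / Pr(P > 450).
- Values: half the sample women; means 415-425 msec (women) and 405-412 msec (men); between-subject SD 15; visit-to-visit SD 8-12; 50 per arm; no drug effect.

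Results across the range:
- women above 450 msec at baseline: about 2-9%
- expected number per arm above 450 msec after baseline: about 0.6-2.7
- share of these already above 450 msec at baseline: about 21-43%
- carry-over subjects per arm: about 0.2-0.8

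A second calculation for 25 women per arm (means 410-425, between-subject SD 15-18, visit-to-visit SD 8-10) gives a share of 26-56% of an expected 0.2-2.5 women. For example, with mean 418 and SDs 15 and 8, 0.73 women are expected above 450 msec, of whom 0.43 are new. Carry-over is 0.73 - 0.43 = 0.30, and 0.30 / 0.73 = 41%.

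**7. Effect of the baseline condition on detecting a shift.** Under the first set of assumptions, a true +8 msec shift adds about 1.1-3.1 subjects per 50 to the planned count and about 1.0-2.6 to the new-onset count. The difference between arms divided by its standard error is about 0.8 to 1.1 either way.

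**The case against.** The strongest reply is that the same section already separates change from level. The woman who stays at 460 msec adds nothing to the > 30 and > 60 msec counts, her change from baseline is zero, and the listing shows both values. Placebo is tabulated alongside, and randomization balances carry-over in expectation, so the row is blurred and not tilted toward an arm. Table 2 is also not an exact precedent, because it merges level and change in one row while the QTcF section reports them apart. All of this stands and makes the point minor. It does not make the > 450 row readable on its own as a count of new events.

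Three stronger readings are tempting, and the documents do not support them.

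- *The ECG output cannot tell a drug effect from the entry distribution.* That could be said of the > 450 row alone. The increase counts, the change summaries and the listing do make the distinction.
- *A true effect is diluted.* The SAP plans number and percent, not a ratio or a test. On that scale the planned contrast is no smaller than the new-onset contrast (step 7 of the working).
- *Single high readings that a triplicate would overturn inflate the count.* Protocol 5.2 does say that, at Screening, "The triplicate QTcF values should be averaged by the Investigator to determine eligibility". Protocol 8.2.3, however, only permits a triplicate when QTcF is slightly above the threshold, and the only limit that the protocol states for women is 470 msec. Nothing stated triggers a repeat for a woman at 455 msec. SAP section 3 also addresses replicates openly: "the average of these evaluations will be used for analysis excluding maximum post-baseline, abnormality, and outlier analyses". That is a deliberate worst-value rule for safety data, not an oversight.

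**Conclusion.** The point holds in a narrow form. The absolute QTcF count at 450 msec ignores baseline, women may enter at 451-469 msec, and nothing else in the SAP corrects the overlap, so unchanged values can be counted and flagged as post-baseline outliers. The 480 and 500 msec rows are unaffected for eligible subjects, and men do not contribute to the overlap.

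That conclusion rests on the text alone. The size does not: the expected carry-over of less than one subject per arm depends on assumed QTcF means and SDs, an assumed half-female sample and a single post-baseline ECG. Severity is minor. This is an improvement in how one descriptive row can be interpreted. It is not evidence of bias between arms, and it gives no reason to question the entry limits or the handling of replicate ECGs.

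**What to change.** In SAP 9.3.2.1, keep the planned counts and add one of the following:

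- beside the > 450 msec count, the number and percent with a post-baseline QTcF > 450 msec among subjects at or below 450 msec at baseline, with that group as the denominator; or
- a table of baseline QTcF category (≤ 450, > 450 to 480, > 480 to 500, > 500 msec) by maximum post-baseline category, by treatment group.

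The second option shows carried-over and new values together and also covers any subject randomized outside the entry limits. The same condition at 480 and 500 msec would be harmless but would change nothing for eligible subjects.

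The cost is one sentence in the SAP and one extra column or small table. It needs no new data and removes no planned output. If it is added after unblinding, SAP section 1 requires that it be identified as post hoc in the study report.
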